3.3 Exclusion Criteria

3.3.1 Patient plans on receiving stem cells from a matched (8/8) related donor.

3.3.2 Patient has used a probiotic dietary supplement within 30 days prior to enrollment. (Consumption of yogurt products is allowed.)

3.3.3 Patient has a history of severe GI tract insult including but not limited to previous bowel perforation, Grade 4 neutropenic colitis or typhlitis, inflammatory bowel syndrome, short small bowel syndrome (Crohn's disease, ulcerative colitis), history of gastrointestinal GVHD, or history of bowel resection.

- 3.3.4 Patient has a medical, psychiatric or social issue that would compromise patient safety or compliance with protocol therapy, or interfere with consent, study participation, follow up, or interpretation of study results.
- 3.3.5 Female patients who are pregnant are not eligible. Women of childbearing potential require a negative pregnancy test prior to enrollment.
- 3.3.6 Patient has diarrhea at the time of enrollment which is *Clostridium difficile* toxin positive.
- 3.3.7 Patient is receiving antibiotic therapy for an active bacterial infection.
- 3.3.8 Patient is allergic to all third or fourth generation cephalosporins, carbapenems, and all aminoglycosides, which are used to empirically treat LBP bacteremia.

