7.1 Required Clinical and Laboratory Evaluations

Studies	Eligibility [§]	First day of conditioning ^{@.&}	Day 0 (Graft Infusion)	Day 7	Day 14	Day 28 or Discharge [%]	Day 56	Day 120
History	X	----	----	----	----	----	----	----
Physical examination, evaluation of GvHD	X	X	X	X	X	X	X	X
Performance status	X	----	----	----	----	----	----	----
Pregnancy test*	X	----	----	----	----	----	----	----
Screening for Clostridium difficile (only if diarrhea at enrollment or first day of conditioning)	X	X ^{&}	----	----	----	----	----	----
Review of LBP administration/patient diary	----	----	X	X	X	X	X	
Blood sample for citrulline and cytokine studies See Section 7.4.1	----	X [^]	X	X	X	X	X ^{a,b}	
Stool sample for correlative studies See Section 7.4.2	----	X [^]	X	X	X	X	X ^b	X ^b

§ All clinical and laboratory studies to determine eligibility must be performed within 7 days prior to enrollment/randomization unless otherwise indicated.

^ Specimen collection on first day of conditioning or anytime within 72 hours before the start of conditioning (prior to chemotherapy). See [Section 7.4.1](#) and [Section 7.4.2](#) for overview of procedures and a Specimen Collection Manual available on the COG protocol web page with further technical detail.

@ The first day of the transplant conditioning regimen is defined as the first day of chemotherapy or TBI, excluding any preceding anti T-lymphocyte antibody therapy. See [Section 4.2.1](#).

% Day 28 or day of discharge, whichever comes first.

* Women of childbearing potential, defined as a female who has had her first menstrual cycle.

& If the patient has diarrhea on the first day of conditioning and repeat stool culture shows *C. diff*, then the patient is ineligible and must be removed from protocol therapy. Reminder: patient condition(s) prior to initiation of protocol therapy must be within parameters required for eligibility. (See [Section 8.1](#))

a Citrulline sample only.

b Blood and stool specimens may be collected within 14 days of the designated time point without being considered a protocol deviation.

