9.0 STATISTICAL CONSIDERATIONS

9.1 Sample Size and Study Duration

Based on estimates from Center of International Blood and Marrow Transplant Research (CIBMTR), approximately 1,400 allogeneic SCTs are performed at COG institutions each year with approximately 25% of them (350 per year) meeting the definition of "alternative donor" as defined in this study. If 30% of those eligible are enrolled, the accrual rate will be about 105 per year. Accounting for start-up time and possible delay of up to 4 months between the two stages of the study, we project accrual to the screening stage within 1.2 years and total accrual duration of 5 years. The sample size of 454 (the first 120 for the screening stage and an additional 334 for the confirmatory stage) may be increased to a maximum of 500 patients (up to 132 for screening stage and an additional 368 for the confirmatory stage) to conservatively account for up to 10% loss due to ineligible or not being randomized to a treatment regimen. Evaluable patients are defined as eligible (or meeting repeated eligibility criteria) randomized patients.

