9.2 Study Design

This is a randomized, double-blind intervention trial evaluating the efficacy of *LBP* in preventing GI aGvHD in children and adolescents undergoing alternative donor HCT.

Patients will be randomized to receive daily *LBP* or placebo using a 1:1 allocation. Randomization will be stratified by stem cell source (cord vs. marrow or PBSC), HLA degree of match (complete match vs. 1 mismatch vs. 2 or more mismatches), and GvHD prophylaxis (ATG/CAMPATH vs. No ATG/CAMPATH). Haplo patients are those who have a related donor with 2 or more HLA mismatches. For stratification, Haplo would be included into the stem cell source. AGvHD outcomes will be assessed from day of stem cell infusion (Day 0) through Day 120. Accrual will be conducted in two stages: a randomized *screening* stage, and a larger *confirmatory* stage. The screening stage will compare the rate of GI aGvHD between the 2 arms at $\alpha=0.30$ (1-sided). After recruitment of 120 patients (up to a maximum of 132 to account for up to 10% loss due to patients deemed to be ineligible or not being randomized to a treatment regimen), the evaluation of the outcome will be assessed. If the screening stage suggests efficacy ($p<0.3$), the study will proceed to the confirmatory stage (N=454). We will use a modified intention-to-treat analytic approach for all evaluable patients. Based on previous CCL studies, we expect the inevaluable rate to be very low.

The primary outcome measure is the incidence of Stage 1-4 GI aGvHD from the day of stem cell infusion (Day 0) through Day 120.

Endpoint incidence is assumed for evaluable patients who are lost to follow up including withdrawal of further data submission and death prior to determination of their outcome (stage 1-4 of GI aGvHD and grade II-IV overall GvHD) in the primary analysis.

Patients who never received conditioning are not at risk of aGvHD and will be considered invaluable for the primary outcome analysis. Patients who have graft failure are not at risk for graft versus host disease, therefore, they will contribute to the primary analysis up to date of graft failure. However, they can still be included in the analysis of toxicity data and laboratory data. See [Section 10.3](#) for definition of graft failure.

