Exploratory Aims 3 and 4: These aims will examine the effects of *LBP* introduction on the intestinal flora of pediatric alloHCT recipients. The association between *LBP* administration and bacterial genes and pathways, and bacterial metabolites will be evaluated with Pearson's correlation coefficient with possible transformation to approximate normality. In addition to confirming the significance, a 95% confidence interval will be estimated for each marker. The total length of the interval depends on the observed correlation; the length will be 0.53 if the correlation is 0.40 and 0.24 if the correlation is 0.8. In addition to correlation, bivariate scatterplots will be used to display the association between *LBP* administration and each marker. Finally, we will perform a descriptive analysis examining the association between GvHD outcomes and bacterial genes, pathways, and metabolites using Cox regression. Additional regression models will adjust for other known GvHD risk factors.

Exploratory Aim 5: This aim will examine the effects of *LBP* on pro-inflammatory cytokines in alloHCT recipients. We hypothesize that *LBP*-associated maintenance or restoration in the microbiota will attenuate serum levels of pro-inflammatory cytokines in the early post-transplant period. We will use the same analytic approach as described for exploratory Aim 2 above.

Exploratory Aim 6: This aim will examine the effects of LBP on the incidence (yes/no) of *Clostridium difficile*-associated diarrhea in alternative donor HCT patients. Patients who have at least one incidence (positive) of *C. diff* during any reporting period is considered evaluable for this aim. We will compare proportion of *C. diff* during the study period between arms via the chi-square test.

Exploratory Aim 7: This aim will examine whether LBP administration reduces hospital days within the first 120 days post hematopoietic cell transplant. Total hospital days over the study period is calculated as the duration between the date of admission for conditional therapy and the date of discharge (or the study end date). Hospital days will be compared between arms by t-test (or Wilcoxon rank-sum test if assumptions for t-test are not met).

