Exploratory Aim 8: This aim will examine the safety of orally administered LBP strains 299 and 299v in alternative donor HCT patients as measured by incidence (yes/no) of *Lactobacillus plantarum* bacteremia. Patients who have at least one incidence (positive) of *Lactobacillus plantarum* during any reporting period is considered evaluable for this aim. We will use the same analytic approach as described for exploratory Aim 6 above.

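### Exploratory Aims 6 and 8 count only patients with a positive result as evaluable, so neither between-arm comparison can be computed as written

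*Combined protocol and SAP*

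**What the plan says.** Section 9.3 introduces the outcomes of Exploratory Aims 6 and 8 as yes/no incidences. Each aim then has a sentence on who is evaluable.

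- Aim 6 (*C. difficile*-associated diarrhea): "Patients who have at least one incidence (positive) of *C. diff* during any reporting period is considered evaluable for this aim". The comparison follows: "We will compare proportion of *C. diff* during the study period between arms via the chi-square test".
- Aim 8 (*L. plantarum* bacteremia, the safety aim in Section 1.2.8): "Patients who have at least one incidence (positive) of *Lactobacillus plantarum* during any reporting period is considered evaluable for this aim". For the method: "We will use the same analytic approach as described for exploratory Aim 6 above".

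Elsewhere the plan uses the word evaluable for a different and workable population. Section 9.1: "Evaluable patients are defined as eligible (or meeting repeated eligibility criteria) randomized patients". Section 9.2: "We will use a modified intention-to-treat analytic approach for all evaluable patients".

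**The concern.** A proportion needs patients without the event in its denominator. The sentences in Aims 6 and 8 admit only patients with the event, and because they apply specifically to these aims they displace the general definition in Section 9.1. Nothing in the plan says that the general definition prevails.

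Two of the eight exploratory aims therefore have no computable comparison as written. One of them is the aim that defines safety for a live bacterial product in transplant recipients. An analyst would have to choose a denominator at the time of analysis, and several are defensible: all eligible randomized patients, those who began conditioning, those who took at least one dose, or those who were tested. The plan should settle that choice in advance.

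**Working it through.** The plan gives no expected rate, power or sample size for Aims 6 and 8, so there is no stated figure to reproduce. The inputs are 60 per arm (screening stage) and 227 per arm (both stages together), from Section 9.4. All event counts below are assumptions. The pilot's 20% rate of *C. difficile* diarrhea (Section 2.5) comes from LBP recipients and is only a guide.

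**1. The rule as written, Aim 6.** Assume 45 positive patients on placebo and 23 on LBP.

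- Evaluable set: 45 + 23 = 68 of 454. Dropped: 454 − 68 = 386, and 386/454 = 85%.
- Proportions: 45/45 = 100% and 23/23 = 100%.
- The expected count in each negative cell is (row total × column total)/N. The negative column total is 0, so both expected counts are 0. The chi-square sum then contains (0 − 0)²/0 and is undefined.

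This does not depend on the counts assumed. At a positive rate r, the rule drops a share 1 − r of patients: 90%, 80% and 70% for r = 10%, 20% and 30%.

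**2. The same counts with all evaluable patients.**

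- 45/227 = 19.8% and 23/227 = 10.1%; difference (LBP − placebo) −9.7 points.
- SE = √[(0.198 × 0.802 + 0.101 × 0.899)/227] = 0.033; 95% CI −16.2 to −3.2 points.
- Pearson chi-square 8.37, p = 0.004.
- At the end of the screening stage, with 12/60 vs 6/60: difference −10.0 points, 95% CI −22.7 to 2.7, chi-square 2.35, p = 0.13.

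**3. Is that set at risk for Aim 6?** Yes, with one refinement. Section 3.3 excludes a patient when "Patient has diarrhea at the time of enrollment which is *Clostridium difficile* toxin positive". A footnote to Section 7.1 repeats the screen: "If the patient has diarrhea on the first day of conditioning and repeat stool culture shows *C. diff*, then the patient is ineligible". *C. difficile*-positive diarrhea at baseline is therefore outside the eligible set. However, Section 9.2 makes patients who never received conditioning inevaluable for the primary outcome only, while Section 8.2 takes them off study. The Aim 6 denominator should say explicitly that they are left out.

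**4. The rule as written, Aim 8.** With 4 cases on LBP and 0 on placebo, the table is 4/4 vs 0/0. With no cases it is 0/0 in both arms.

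**5. Aim 8 with a full denominator.**

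- 4/227 = 1.8%, exact 95% CI 0.48% to 4.45%, against 0/227.
- 0/n: one-sided 95% upper limit 1 − 0.05^(1/n) = 1.3% for n = 227 and 4.9% for n = 60. The upper end of the two-sided exact 95% interval is 1 − 0.025^(1/n) = 1.6% and 6.0%.
- Choice of test: for 4/227 vs 0/227, uncorrected chi-square gives p = 0.045 and Fisher's exact test p = 0.12. Fisher's p first falls below 0.05 at 6 vs 0 (p = 0.030; 5 vs 0 gives 0.061). With counts this small, chi-square is unreliable.

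**The case against.** The strongest reply is that nobody would follow the sentence literally. Both outcomes are labelled yes/no, both aims speak of an incidence, and only one reading gives a computable analysis: at least one positive result makes a patient an event. Section 9.1 supplies a denominator, and the test would fail visibly on an empty column. Much of this stands. The sentence is probably a slip, and the 100% vs 100% table shows what the rule implies; it does not predict what would be reported. But evaluable is a population term in this plan, the sentence redefines it for each of these aims, and the choice among plausible denominators remains open.

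A reader might infer three stronger things that the documents do not support.

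- *That patient safety is left unmonitored.* Section 4.2.3 stops study product after any LBP-positive blood culture and requires a report within 24 hours. Section 11.9 starts a sequence of monitoring events, and Section 12.2 gives the DSMC review of toxicity. What is missing is a planned rate and comparison; individual cases would still be detected.
- *That bloodstream infection in general lacks an arm comparison it was promised.* Section 9.2 lists BSI as an exploratory endpoint, but this is plausibly the mucosal-barrier infection of Aim 2, which Section 7.3.1 abbreviates MBI BSI and Section 9.3 compares by Cox regression. The descriptive analysis in Section 9.3 may also cover counts by arm. Adding an all-BSI comparison would be a preference and would not correct an error.
- *That the SAE reporting rules contradict one another.* Section 11.5 says that protocol-specific guidelines supersede the general ones, so the narrower instructions in Section 11.9 can be read as permitted exceptions.

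**Conclusion.** The point holds as a wrong stated rule in two exploratory aims. Read literally, neither comparison can be computed at any event rate, and the most favorable safety result, no bacteremia, leaves no one to analyze. This conclusion follows from the text alone; the numerical examples rest on assumed counts and serve only as illustration.

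The practical consequence is limited. The intended meaning is fairly plain, the aims are exploratory, and the primary aim, the sample size, the screening-stage decision and expedited safety reporting are untouched. The sentences should still be corrected before unblinding, because the denominator of the safety aim should not be chosen after the data are seen.

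**What to change.** In Section 9.3, replace the two evaluability sentences, and for Aim 8 the cross-reference to Aim 6 as well.

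1. **Aim 6:** *All evaluable (modified ITT) patients who began conditioning form the denominator. Those with one or more positive reports of C. difficile-associated diarrhea in any reporting period are counted as events.* The chi-square test can stay.
2. **Aim 8:** *All evaluable (modified ITT) patients who received at least one dose of study product form the denominator. Those with one or more blood cultures positive for L. plantarum in any reporting period are counted as events. Arms are compared by Fisher's exact test, and the rate in each arm is given with an exact 95% CI.*

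The restriction to blood cultures matters. Stool is also examined for LBP (Section 7.3.2), and 21 of 22 sampled pilot patients had *Lactobacillus*-positive stool (Section 2.5). A looser phrase such as any positive result could count gut colonization as bacteremia.

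Cost: a wording change only. Bloodstream infection and *C. difficile* diarrhea are already collected through Day 120 under Section 7.2, so no visits, samples or patients are added. There are two small drawbacks: Fisher's test is slightly conservative, and the dosed set may omit a few randomized patients.

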1.2 Exploratory Aims

- 1.2.1 To determine whether orally-administered *LBP* decreases the incidence of Grade II–IV aGvHD following alternative donor alloHCT.
- 1.2.2 To determine whether *LBP* administration maintains intestinal integrity as measured by mean serum citrulline levels and reduction in mucosal barrier injury (MBI) bacteremia.
- 1.2.3 To measure the effects of *LBP* on the intestinal flora phylogenetic composition during and after alternative donor alloHCT using 16S rRNA gene deep sequencing.
- 1.2.4 To measure effects of *LBP* on intestinal flora function during and after alternative donor alloHCT using metagenomic and metabolite profiling.
- 1.2.5 To measure proposed immunomodulatory effects of *LBP* in mean serum levels of allereactive-induced inflammatory cytokines (IL-2, IL-6, IL-12p70, IFN γ , TNF α , etc.) in patients receiving *LBP* compared to placebo.
- 1.2.6 To determine whether *LBP* administration reduces the incidence of *Clostridium difficile*-associated diarrhea in alternative donor HCT patients.
- 1.2.7 To determine whether *LBP* administration reduces hospital days within the first 120 days post hematopoietic cell transplant (HCT).
- 1.2.8 To define the safety of orally administered *LBP* strains 299 and 299v in alternative donor HCT patients as measured by incidence of *Lactobacillus plantarum* bacteremia.

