9.4 Power and Sample Size

Primary Aim: Review of the literature suggests that the incidence of GI aGvHD ranges from 15% to 45% across various studies; therefore a precise estimate of baseline GI aGvHD incidence for this study population is not available. The incidence of GI aGvHD was 27% in the control arm of the most recent COG trial (ASCT0431), which enrolled a patient population where 54% of patients received grafts from matched sibling donors. We anticipate a higher rate of GI aGvHD in the control arm of this trial, as we are including only alternative donor recipients (refer to eligibility criteria), and therefore project the baseline cumulative GI aGvHD incidence through Day 120 to be at least 30%. Success will be defined as a 40% relative reduction in the cumulative incidence of GI aGvHD (i.e., 18% in LBP arm vs. 30% in placebo arm). A sample size of 120 (60 per arm) for the screening stage and 454 (227 per arm) for the confirmatory stage (including patients randomized during the screening stage) will provide 85% power to detect an effect size of 40% relative reduction at 1-sided $\alpha=0.3$ and 0.05, respectively in a two-sample test of binomial proportions. The overall power of the study, which is the probability of establishing efficacy in the primary endpoint in both analyses, is lower than the power for each component separately and higher than the product of two. Based on simulations, the overall power is at 80% in this scenario. The overall type I error for the design is also slightly reduced from the type I error of 0.05 for each individual component if they are analyzed separately. Based on simulations, the overall type I error is at 0.035.

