Exploratory Aims 1 and 2: The sample size for the primary aim drives the overall accrual goal and thus the number of subjects available for the exploratory aims. These endpoints will be analyzed only at the end of the study, either at the end of the screening stage or confirmatory stage. Therefore, the power is estimated for the two situations separately based on sample size of 120 (60 per arm) or 454 (227 per arm) without any adjustment for power after the confirmatory stage. For Exploratory aim #1, a baseline rate of Grade II–IV aGvHD in the range of 30%–50%, the sample size after confirmatory stage is sufficient to detect a 15% reduction in aGvHD rate, while the sample size after screening stage is sufficient to detect a 20% reduction in aGvHD rate with LBP compared to placebo. Power estimation is based on 2-sample test of proportions at $\alpha=0.05$ (2-sided). For Exploratory aim #2 on serum citrulline levels, the sample size after confirmatory stage is sufficient to

detect an effect size of 0.4 standard deviation (SD), assuming we obtain samples from 80% or more of the subjects; on the other hand, the sample size after screening stage is sufficient to detect an effect size of 0.7 SD if we obtain samples from $\geq 80\%$ subjects. Power estimation is based on two-sample t-test at $\alpha=0.0125$ (2-sided), where α is based on the Bonferroni adjustment for the 4 parallel comparisons with an overall $\alpha=0.05$.

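### The only safety analysis with a named test (Exploratory Aim 8, L. plantarum bacteremia) is a between-arm difference test with no upper bound, so a non-significant result cannot define the safety of LBP

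*Combined protocol and SAP*

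**What the plan says.** Section 1.2.8 sets out to establish the safety of the two LBP strains "in alternative donor HCT patients as measured by incidence of" L. plantarum bacteremia. Section 9.3, Exploratory Aim 8, repeats that safety is "measured by incidence (yes/no) of *Lactobacillus plantarum* bacteremia", and then gives two rules.

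- **Who counts:** "Patients who have at least one incidence (positive) of *Lactobacillus plantarum* during any reporting period is considered evaluable for this aim".
- **How it is analysed:** "We will use the same analytic approach as described for exploratory Aim 6 above". The Aim 6 text reads: "We will compare proportion of *C. diff* during the study period between arms via the chi-square test".

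Neither aim states a significance level, sidedness, continuity correction, acceptable rate, margin or interval. Section 9.4 gives power only for the primary aim and Exploratory Aims 1 and 2. By contrast, the text for Exploratory Aims 3 and 4 in 9.3 commits to a 95% confidence interval for each bacterial marker and states its expected length.

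Other safety provisions exist without a statistical method. Section 9.2 mentions an analysis of toxicity data. Sections 9.5 and 12.2 provide for periodic DSMC review, including toxicity. Sections 4.2.3 and 11.9 require every LBP-bacteremia to be reported within 24 hours and the patient to come off protocol therapy; 11.9 adds that the report sets further monitoring in motion.

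**The concern.** A chi-square test asks whether the arms differ. Aim 8 asks how safe the product is, which is a question about how large the LBP-arm rate could be. Failing to find a difference does not answer it, especially for a rare event. The figure a reader needs is the highest LBP-arm rate that the data exclude, and the p-value does not give it.

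If the p-value is the only inferential result, a report could present a non-significant comparison as reassurance when that outcome was likely even with a real excess of bloodstream infection in heavily immunocompromised children. The weakness is greater if the trial ends after the screening stage.

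**Working it through.** **No plan figure to reproduce.** The text available for review states no rate, power or precision for Aim 8. Part of the pilot report in 2.5 was not available, so a pilot rate may exist there.

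**Inputs from the plan**
- Size per arm, from 9.4: "A sample size of 120 (60 per arm) for the screening stage and 454 (227 per arm) for the confirmatory stage".
- Method: Aim 6 chi-square (9.3).

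**Assumptions**
- No placebo-arm cases.
- A true LBP-arm rate of 1% (range shown below).
- Two-sided 0.05, which 9.4 states only for Exploratory Aim 1.
- No continuity correction.
- All treated patients in the denominator, taken as 227 or 60 per arm.

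**Step 1: the denominator as written.** If only patients with a positive result are evaluable, every evaluable patient is an event. The proportion is 100% in any arm with a case, there is no contrast, and the test cannot be computed. Everything below assumes this has been corrected.

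**Step 2: cases needed for significance.** For k LBP cases against 0, with n per arm, the uncorrected statistic reduces to 2nk/(2n − k).
- n = 227, k = 3: 454 × 3/451 = 3.02, p = 0.082.
- n = 227, k = 4: 454 × 4/450 = 4.04, p = 0.045.

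So 4 against 0 is needed. At n = 60 it is also 4 (120 × 4/116 = 4.14, p = 0.042; 3 against 0 gives p = 0.079). With the Yates correction or two-sided Fisher, 6 against 0 is needed at both sizes.

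**Step 3: chance of a non-significant result at a true 1%, n = 227.** Expected cases are 227 × 0.01 = 2.27.

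P(X ≤ 3) = 0.102 + 0.234 + 0.267 + 0.203 = 0.806.

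| Version of the test | Cases needed against 0 | Non-significant at 1% |
|---|---|---|
| Uncorrected, one-sided | 3 | 60.4% |
| Uncorrected, two-sided | 4 | 80.6% |
| Fisher, one-sided | 5 | 92.1% |
| Yates or Fisher, two-sided | 6 | 97.2% |

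With a placebo rate of 0.1% instead of zero, the uncorrected two-sided figure is 84.4%.

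**Step 4: other true rates (uncorrected, two-sided, no placebo cases)**

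| True LBP-arm rate | n = 227 | n = 60 |
|---|---|---|
| 0.5% | 97.2% | 99.98% |
| 1% | 80.6% | 99.7% |
| 2% | 33.3% | 96.8% |
| 3% | 8.9% | 89.4% |
| 5% | 0.3% | 64.7% |

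**Step 5: what an exact bound would give.** With no cases, the one-sided 95% upper bound is 1 − 0.05^(1/n).
- 0/227: 1.31%.
- 0/60: 4.87%.
- 3/227 (Clopper-Pearson): 3.38%, from data that the two-sided test would call non-significant.

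**The case against.** **Aim 8 is not the trial's whole safety provision.** A reader might infer that it is, and the documents do not support that. Toxicity analysis (9.2), DSMC review (9.5, 12.2) and routine collection of attributable Grade 3 and higher events (11.10) are all stated. Nor would three cases against none pass unnoticed: 4.2.3 and 11.9 trigger reporting and action for each case whatever the test shows. This stands. It limits the point to the final inference, because none of these provisions says what rate the completed trial has excluded.

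**The plan never equates non-significance with safety.** That is correct. Section 1.2.8 speaks of incidence, and 9.3 promises counts and percentages for categorical variables, so a reader could compute a bound. What is missing is a commitment to report one and a guard against misreading the p-value.

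**The comparator has value.** Section 7.3.2.1 reports detectable LBP in 24 of 230 adult transplant patients at baseline and expects somewhat more in children. Sections 3.3.2 and 4.3.1 allow yogurt, and the endpoint is defined at species level. Background cases are therefore possible in either arm, and the randomized comparison helps attribution. This stands: the comparison should be kept, but not as the basis of the safety conclusion.

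**Sixty per arm is not an automatic end point.** The 9.4 wording on analysis "either at the end of the screening stage or confirmatory stage" might be read as covering Aim 8, but it concerns Exploratory Aims 1 and 2. Under 9.5 a failed screening stage goes to the DSMC for consideration of early termination. Sixty per arm is a possible final size, no more.

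**The aim is exploratory.** It is, and that bears on priority. It does not make a difference test answer a question about an absolute rate.

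**Conclusion.** The point holds in this form: the one safety analysis with a named test is a difference test with no bound, margin or power, and a non-significant result from it cannot define the safety of LBP.

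The 81% figure is conditional on the assumptions listed in the working and is not a property of the plan alone. The choice of test version moves it between 60% and 97% at the same 1% rate. At a true 3% or more with 227 per arm, the uncorrected two-sided test would usually detect the excess; with 60 per arm it would still miss 3% in 89% of trials.

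The positives-only definition of evaluable is the more basic defect and must be corrected first, since no test or bound has a valid denominator without it. Correcting it alone leaves this problem in place. The change is worth making because it is cheap; it does not touch the primary analysis.

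**What to change.** In 9.3, Exploratory Aim 8, replace both the sentence defining evaluable patients and the final sentence with:

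> All randomized patients who received at least one dose of study product are evaluable. The incidence of L. plantarum bacteremia will be reported by arm, and the LBP-arm incidence will be given with its exact (Clopper-Pearson) one-sided 95% upper bound. The between-arm comparison will be reported as supportive information on attribution, and a non-significant difference will not be interpreted as evidence of safety.

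Add to 9.4 that zero cases would exclude LBP-arm rates above about 1.3% with 227 patients and about 4.9% with 60, and that the reported bound will use the number actually treated.

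The cost is a few sentences, with no new data or patients. The downside is a more modest safety statement, especially if the trial ends after the screening stage.
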